**6. Have you been working with a statistician in designing this protocol?**

Consultation with a professional statistician is highly recommended to ensure good science of the study and facilitate the review process.

Answer/Response: Yes

**IF YES, what is their name?**

Answer/Response: [name]

**7. Will data from multiple sites be combined during analysis?**

Answer/Response: No

INSTRUCTIONS: IF YES, answer the following questions

**7(a). Does the study involve randomization?**

Answer/Response:

**IF YES, will randomization be done at each site or among sites?**

Answer/Response:

**7(b). Has the sample size calculation considered the variation among sites?**

Answer/Response:

**7(c). When combining the data from multiple sites to assess the study results, is the effect of the treatment to be tested (or the association to be tested) assumed to be the same across sites or vary among sites? What is the modelling strategy?**

Answer/Response:

**7(d). Is there a common protocol used in all sites?**

Answer/Response:

**IF NO, how will differences among sites, such as those related to the implementation, inclusion criteria, patient characteristics, or other sites characteristics, be considered to assess the study results?**

Answer/Response:

**Study Procedures-Biomedical Research**

**1. What will be done in this protocol?**

**INSTRUCTIONS:**

This should include everything that will be done as part of this protocol. Do not repeat information that is included in other sections such as Background or Hypothesis sections.

This section should include an indication of which research interventions if any offer a prospect for direct benefit and which interventions (invasive measurements, collection of blood, tissue, data, surveys, etc.) are being done solely to answer a research question and generate generalizable knowledge. If the interventions done solely for research purposes are associated with greater than minimal risk they need to be justified.

Describe and justify any control and experimental arm and include method, dose, and duration of drug administration. Reference any claim of clinical equipoise if applicable.

If you are obtaining specimens or data, provide information regarding the type of specimen/data, amount of specimen needed and how the specimen/data will be obtained and what analysis will be done with the specimen/data.

Special note for studies with waiver of consent/waiver of documentation of consent:

Include a statement regarding how subjects will be recruited. For other studies this information is captured in Recruitment does not need to be duplicated in this section.

Answer/Response:

The parent/ legal guardian will be consented at a clinic or hospital visit prior to surgery by study staff and will include the Peds Cardiac NP they are familiar with when possible. Subjects will be monitored for 48 hours for the need for fibrinogen supplementation

Once the need for fibrinogen supplementation is confirmed in the OR or PICU, subjects will be randomized into one of two treatment groups (n=15 in each group):

1. Cryoprecipitate group (dose: 10 ml/kg; active control group) or
2. Fibrinogen Concentrate group (dose: 70 mg/kg; intervention group) single dose.

Administration of the study drug is via transfusion.

There will be no placebo group since withholding treatment is neither consistent with standard of care nor acceptable ethically.

No other aspects of care will be modified.

In the event that a second round of fibrinogen supplementation is required (bleeding with documented hypofibrinogenemia) participants will receive either FC or cryoprecipitate based on their initial randomization. If any additional fibrinogen supplementation is then needed (after the first 2 supplementation doses), cryoprecipitate will be administered to all subjects per standard of care (including those who received FC).

Data to be obtained:

1. Demographic/preoperative data: collected from the medical record
  - age in days/months (all patients to be younger than 24 months)
  - gender
  - weight
  - preoperative diagnosis
  - surgery type & date (Norwood, arterial switch, truncus arteriosus, Glenn, Fontan, TAPVR, AV canal, tetralogy of Fallot, etc)
  - preoperative standard of care labs PT/aPTT/INR/hgb level/ hematocrit/ platelet count/

fibrinogen level (if exists)/ creatinine

2. Intra-operative Data: collected from the medical record

- CPB time & aortic cross clamp time
- use of hypothermic circulatory arrest (ice packs placed on the head)
- was post-CPB ultrafiltration performed?
- Platelet count prior to separation from CPB
- was ATIII administered? (thrombate)
- Transfusion requirements: PRBC/Cell Saver/FFP/PLT/ cryo - to be collected as number of units per each product, not volume. (for PLT - was it pooled PLT or single donor apheresis, if possible)
- was rFVIIa given (factor seven, novoseven). Please pay attention - the fact that rFVIIa was ordered DOES NOT mean that was actually administered as we order factor VII for ALL big cases (to have available in the OR) but not necessarily administer it
- Need for ECMO
- Was the chest left open? (always in ECMO, but open chest does not necessarily mean ECMO)

ROTEM (clotting labs) will be drawn for research purposes after admission and after administration of the study treatment: Extem (CT/A10/A20/MCF); Fibtem (A10/A20/MCF) and fibrinogen. The blood drawn for this will be obtained through an existing line, put into place as part of the subject's usual care.

3. Postoperative Data (PICU, up to 48 hours after surgery) collected from the medical record

- admission PT/aPTT/INR/platelet count/ fibrinogen level/ hgb level/HCT level (could be obtained from initial ABG)
- Bleeding (Chest drain/s output)
- Need for additional transfusion (PRBC/cell saver/FFP/platelets/cryoprecipitate). Will need to know, if possible, whether transfused from same unit that was already exposed to in the OR or new unit (= new exposure)
- Factor VIIa administration
- re-exploration? (= starting ECMO in the PICU)
- delayed chest closure? (will answer whether went to PICU with chest open)

**2. If this protocol involves study treatment, explain how a subject will be transitioned from study treatment when they have completed their participation in the study.**

**Example:** If the subject will be taking an investigational drug, will they need to be put back on an approved drug when they have completed the study? If yes, explain how this will be accomplished and who will cover the cost. If the subject has a device implanted will it be removed? Again- who will cover the cost of the removal?

**Instructions:** Answer NA if this study does not involve a study treatment.

Answer/Response: There is no transition from study treatment.

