### Objectives/Hypothesis

#### INSTRUCTIONS:

If this study involves biomedical research clearly state the objectives and hypotheses and clearly define the primary and any secondary outcome measures. If this study involves qualitative research clearly state your research hypothesis or question.

This section should not include information already included in other sections such as background information or information from the procedures section.

Answer/Response: Our hypothesis is that fibrinogen concentrate will be as effective as cryoprecipitate in achieving adequate hemostasis after separation from CPB in pediatric cardiac surgery patients.

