### **4. What is your plan for primary variable analysis?**

Include primary outcome(s)/predictor variable(s), statistical methods/models/tests to be employed, or descriptive summaries as appropriate. If not applicable, please provide explanation.

Answer/Response:

Outcomes: the primary outcome of the study will be any allogeneic blood transfusion within the first 24 hours after administration of the FC or cryoprecipitate.

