### **5. What is your plan for secondary variable analysis?**

Include the following:  
--Secondary outcome(s)/predictor variables, statistical methods/models/tests to be employed, or descriptive summaries as appropriate. If not applicable, please provide explanation.  
--For phase III studies, the power/precision of the study to address the secondary objective(s).

Answer/Response: Secondary outcomes will include: administration of individual blood products (RBC, platelets, FFP, cryoprecipitate) over the initial postoperative 48 hours and up to 7 days after surgery, bleeding over the first postoperative 48 hours (intraoperatively = cell saver volume; postoperatively = chest drain/s output), the need for surgical re-exploration for hemostasis over the first postoperative 48 hours, the use of recombinant factor VIIa as rescue for refractory bleeding in the first 48 postoperative hours, length of ICU stay, hospital length of stay, thromboembolic complications over the first seven postoperative days and a 30-day composite of AKI, stroke, severe myocardial dysfunction or myocardial infarction, sepsis and

mortality (or until discharge whichever is earlier).

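### Unblinded ordering without written transfusion triggers, and a repeat randomized dose that can count in the control arm only, limit what the 24-hour transfusion outcome says about haemostatic efficacy

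*Combined protocol and SAP*

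**What the plan says.** The hypothesis (Objectives/Hypothesis) is that "fibrinogen concentrate will be as effective as cryoprecipitate in achieving adequate hemostasis after separation from CPB". The primary outcome (Statistical Considerations, question 4) is "any allogeneic blood transfusion within the first 24 hours after administration of the FC or cryoprecipitate". It does not list the products that count, and it does not say how a repeat study dose is handled.

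Randomization is 1:1 and unblinded (Statistical Considerations, question 1). The study team, anesthesiologist or PICU staff give the product and chart it (Subject Compliance with Study Procedures). Other treatments are unrestricted (Inclusion/Exclusion Criteria, question 3). Under Study Procedures, question 1, "No other aspects of care will be modified". The only numeric threshold for giving a product is the FIBTEM criterion for entry. No threshold is given for red cells, platelets or FFP.

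On re-dosing, Study Procedures says: "In the event that a second round of fibrinogen supplementation is required (bleeding with documented hypofibrinogenemia"; in that case "participants will receive either FC or cryoprecipitate based on their initial randomization". Beyond two doses, "cryoprecipitate will be administered to all subjects per standard of care (including those who received FC".

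Two lists show what is treated as a blood product. The secondary outcomes include "administration of individual blood products (RBC, platelets, FFP, cryoprecipitate) over the initial postoperative 48 hours". The postoperative data items include "Need for additional transfusion (PRBC/cell saver/FFP/platelets/cryoprecipitate". FC is in neither.

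**The concern.** There are two separate issues.

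**Ordering.** The outcome is a clinical decision rather than a measurement. Staff who know the arm can be expected to make or influence it, and no common rule is written. If a clinician's threshold for giving platelets or FFP depends on which fibrinogen product was used, the arms can differ without any difference in haemostasis. This could go in either direction.

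**Counting.** Take two infants, one per arm, with the same continued bleeding and the same documented low fibrinogen within 24 hours of the first dose. The control infant receives cryoprecipitate, which is on the product lists. The other receives FC, which is not. If the outcome is read with those lists, one infant has an event and the other does not, although the haemostatic result was the same. Equal re-dosing need would then favour FC. This follows from the written rules and needs no assumption about clinicians' behaviour. It is confined to the second dose: the first is probably outside a window that opens after administration, and the third and later doses are cryoprecipitate in both arms.

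At stake is the interpretation of a transfusion difference. It could be read as haemostatic efficacy when part of it reflects ordering habits or the label on the repeat product.

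**Working it through.** **The plan's own figure.** Statistical Considerations, question 2 gives 30 infants (15 per arm) for a difference of 2 products, 80% power and α = 0.05, including 20% dropout. No SD is stated. Taking α as two-sided, n per arm = 2 × (1.96 + 0.84)² × SD² / 2², rounded up:
- SD 1.5: 9 per arm, 18/0.8 = 22.5, so 23 in total.
- SD 1.7: 12 per arm, 24/0.8 = 30.
- SD 2.0: 16 per arm, 32/0.8 = 40.

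The figure of 30 therefore implies an SD near 1.7, but cannot be confirmed. If all 15 per arm are analysed, a two-sample t test has 80% power for 2 products at SD 1.89 (standardized difference 2/1.89 = 1.06).

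**Assumptions for the rest.** The documents give no event rate, ordering shift or second-dose rate, so every rate below is assumed for illustration. Throughout: 15 per arm, two-sided 0.05, no true haemostatic difference. Yes/no results are exact enumerations over both binomials. Both tests are shown because the plan allows either.

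**Ordering, yes/no scale (chance of a significant result)**

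| Arms (%) | Fisher | Pearson |
|---|---|---|
| 60 v 60 | 1.6% | 4.9% |
| 80 v 80 | 1.7% | 5.0% |
| 90 v 90 | 0.6% | 2.5% |
| 60 v 50 | 3.3% | 7.9% |
| 80 v 70 | 4.0% | 10.2% |
| 90 v 80 | 4.1% | 10.1% |
| 60 v 40 | 9.5% | 18.3% |
| 80 v 60 | 11.2% | 23.3% |
| 90 v 70 | 14.9% | 27.8% |

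A 10-point shift stays below 5% by Fisher, although the estimate itself moves by 10 points.

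**Second dose, yes/no scale.** Let p be the chance of any other counted product, equal in both arms, and r the chance that an otherwise untransfused control infant has a second dose in the window. The control rate is p + (1 − p)r and the FC rate is p.

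| p | r | Control v FC (%) | Fisher | Pearson |
|---|---|---|---|---|
| 0.60 | 0.2 | 68 v 60 | 2.7% | 7.5% |
| 0.60 | 0.5 | 80 v 60 | 11.2% | 23.3% |
| 0.80 | 0.2 | 84 v 80 | 2.0% | 5.5% |
| 0.80 | 0.5 | 90 v 80 | 4.1% | 10.1% |
| 0.90 | 0.2 | 92 v 90 | 0.5% | 2.3% |
| 0.90 | 0.5 | 95 v 90 | 0.6% | 2.8% |

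The gap is (1 − p)r, so it shrinks as p rises. At p = 0.90 the rejection rates are about those with no bias.

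**Second dose, product-count scale.** The sample-size statement counts products, and there a high base rate sets no ceiling. If 20% to 50% of all controls have one extra counted product, the mean shift is 0.2 × 1 = 0.2 to 0.5 × 1 = 0.5 product. Against the target this is 0.2/2 = 10% to 0.5/2 = 25%. By noncentral t with 15 per arm, rejection is 5.9% to 10.8% at SD 1.89 and 5.4% to 7.3% at an assumed SD of 3.0. With 12 analysed per arm and the matching SD of 1.67, it is again 5.9% to 10.8%.

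**The case against.** The strongest reply is that counting repeat cryoprecipitate is intended. The Background gives fewer allogeneic transfusions as a goal, the sizing target is exposure to additional allogeneic products, and the postoperative data items ask whether each unit is a new exposure. If the target is exposure, avoiding repeat cryoprecipitate is part of FC's benefit. This stands. A reader might infer that the primary outcome is wrong and must be redefined; the documents do not support that. Excluding repeat doses altogether would also have a cost, because re-dosing for continued bleeding is itself a sign of haemostatic failure.

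Second, the one-arm count is an inference. The primary outcome lists no products, Study Procedures says the study drug is given by transfusion, and FC is human-derived. The Background does contrast FC with allogeneic blood products, so the inference is plausible. Still, this is an ambiguity in the definition rather than a stated rule.

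Third, discretionary ordering is common to open-label transfusion trials. This one is single-centre, with usual care unchanged in both arms. A reader might infer that clinicians will order differently, or in FC's favour. Nothing in the documents shows either, and even that the treating staff place the orders is inferred from usual care. What stands is that the same policy need not be applied equally when the arm is known and no trigger is written.

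Fourth, this is a pilot that already collects drain output, cell-saver volume, re-exploration and post-treatment ROTEM. These help to interpret a transfusion difference but do not prevent one. The plan also specifies hypothesis tests and claims power, so pilot status does not dispose of the point.

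**Conclusion.** The point holds in a limited form. Arm-dependent ordering is possible and not demonstrated. The counting asymmetry follows if the outcome is read with the protocol's own product lists, and it is confined to a second randomized dose within 24 hours. Counting that dose is legitimate as allogeneic exposure, but the resulting difference is not evidence that FC is as effective haemostatically.

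The size cannot be fixed from the documents. On the yes/no scale the second-dose effect is negligible if most infants are transfused anyway. It reaches 11.2% Fisher rejection only at a 60% base rate with half of the otherwise untransfused controls re-dosed. On the count scale it is 0.2 to 0.5 product, or 10% to 25% of the target, if 20% to 50% of controls have one extra counted product. A reader might infer that the false-positive rate is materially inflated; that needs the larger assumed shifts, and no stated rate supports them. Rejecting no difference is also only an indirect measure for a hypothesis of being as effective. This is a cheap improvement worth making, not a fatal flaw.

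**What to change.** **(a) Outcome definition.** In Statistical Considerations, question 4, state whether repeat randomized doses count. Pre-specify the 24-hour outcome both with and without the first two randomized fibrinogen doses, handled identically in both arms. Cryoprecipitate given as a third or later dose counts in both versions. Base the haemostatic-efficacy conclusion on the version without the two doses, together with the proportion in each arm needing a second dose, so that re-dosing stays visible. The version with them describes allogeneic exposure. The sole primary outcome need not be redefined.

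**(b) Ordering.** Before enrolment, write down the unit's usual red cell, platelet and FFP triggers as one set for both arms. Allow documented clinical override and record the indication for each product given in the 24-hour window.

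**Cost.** A few sentences in the protocol, a short trigger list and one indication field per product. Almost all of the data are already collected. Charting increases a little and clinicians lose a little discretion; if the unit has no written triggers, the team must agree them first. Override leaves some discretion in unblinded hands, so ordering bias is reduced, not removed. Sample size, arms and doses do not change.

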FC is a lyophilized, nano-filtered and pathogen reduced and inactivated human fibrinogen concentrate with a constant content of 900-1300 mg/vial (final concentration 20g/L). While cryoprecipitate is still in use in North America, it is not available in Europe (except for the UK) due to safety concerns, as it does not undergo pathogen reduction and inactivation. FC has several important potential advantages over cryoprecipitate including: standardized fibrinogen content, higher purity, faster preparation without need for blood bank processing or cross-matching (which also eliminates the risk of human-related transfusion errors), improved safety via pathogen reduction, avoidance of transfusion related acute lung injury (TRALI) and significantly decreased volume of transfusion (which may be particularly important in children with congenital heart diseases as they may be intolerant to excessive volume overload). Yet, cryoprecipitate may be a better hemostatic agent as it also contains factors VIII and XIII, fibronectin, von Willebrand factor and platelet microparticles, all of which are important for normal hemostasis in bleeding patients. Hence it is not known whether FC will provide hemostatic efficacy similar to cryoprecipitate in bleeding pediatric cardiac surgery patients.

Initial studies evaluating the use of FC in cardiac surgery patients reported conflicting results. Surprisingly, several studies failed to report a benefit with the use of FC mainly due to enrollment of patients who did not have low fibrinogen levels. A recent large randomized controlled study in adult cardiac surgery patients, however, demonstrated non-inferiority of FC compared to cryoprecipitate in bleeding cardiac surgery adult patients with low fibrinogen levels (and as a matter of fact FC was found to be superior over cryoprecipitate in regard to several outcome measures). Hence it seems that FC may be a better alternative for fibrinogen supplementation in bleeding cardiac surgery patients compared to cryoprecipitate.

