**INSTRUCTIONS:**

The stratification factors and/or the randomization plan should be identified. If there is no randomization component or important patient characteristics that will be used in treatment allocation or data analysis, a statement to this effect should be included.

Stratification factors: These are pretreatment patient characteristics which could be balanced across treatment arms by design or may be used to determine starting dose or treatment allocation.

If randomization is going to be used, the details of the randomization plan should be described.

The description should include:

- the method and timing of randomization
- the type of randomization scheme that will be used in the study
- whether or not the randomization masked/blinded/if so, then to whom is it masked/blinded
- who has access to the randomization scheme

Answer/Response:

- Once the need for fibrinogen supplementation is confirmed after separation from CPB, patients will be randomized into one of two treatment groups (n=15 in each group):
  1. Cryoprecipitate group (dose: 10 ml/kg; active control group) or
  2. Fibrinogen Concentrate group (dose: 70 mg/kg; intervention group).
- 1:1 randomization unblinded using a computer generated randomization list

► IF YES, who will generate the randomization scheme?

\_\_\_\_\_ Sponsor

\_\_\_\_\_ UVa Statistician.  Insert name Answer/Response:

\_\_\_\_\_ UVa Investigational Drug Service (IDS)

\_\_x\_\_ Other:  Specify Answer/Response: computer generated by the CRC

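### Intra-operative bleeding is defined as cell saver volume, but the data list records cell saver in units and not volume, so that component of the secondary bleeding outcome has no input

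*Combined protocol and SAP*

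**What the plan says.** Statistical Considerations, item 5 (secondary variable analysis), lists as one outcome "bleeding over the first postoperative 48 hours (intraoperatively = cell saver volume; postoperatively = chest drain/s output". The intra-operative component is therefore a volume of cell saver blood and the post-operative component is drain output.

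Study Procedures, item 1, Intra-operative Data, gives the rule for abstraction: transfused red cells, cell saver, FFP, platelets and cryoprecipitate are "to be collected as number of units per each product, not volume". Cell saver is named inside that rule. No other line of the intra-operative list mentions cell saver or any measure of blood loss.

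Postoperative Data, in the same item, carries the other component, "Bleeding (Chest drain/s output". For later transfusions it lists the products, again including cell saver, without a unit of measure. It adds: "Will need to know, if possible, whether transfused from same unit that was already exposed to in the OR or new unit".

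The Background gives as one advantage of fibrinogen concentrate a "significantly decreased volume of transfusion (which may be particularly important in children with congenital heart diseases". Weight is among the demographic items to be collected.

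**The concern.** An outcome definition and its data list have to match before the first infant is enrolled. Here the definition asks for a volume and the list excludes volume for the same item by name. If the form is built from the list, the intra-operative bleeding component will be missing for every participant. It could then be recovered only by returning to the charts, with the measurement chosen after the data have been seen.

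There is a smaller, related matter. All participants are under 24 months, and the post-operative item shows that the investigators expect one unit to serve more than one transfusion. A count of units then records how many donors the infant met, but not how much was given from each. The plan does not say how part-units are counted. The reduced transfusion volume named in the Background could not be examined across all products if intra-operative volumes are left out.

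**Working it through.** The plan attaches no figure to this point, so there is none to reproduce. The main check is a comparison of texts.

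**1. Definition against data list**

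| Component of the bleeding outcome | What item 5 requires | What the data list collects | Computable? |
|---|---|---|---|
| Intra-operative | Cell saver volume | Cell saver as number of units, volume excluded | No |
| Post-operative | Chest drain output | Chest drain output | Yes |

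One of two components lacks its input. A unit of cell saver blood is not defined anywhere, so the count cannot be converted to ml.

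**2. What is not touched.** The primary outcome (item 4) is any allogeneic transfusion within 24 hours of study product. As worded this is yes or no, and is the same whether units or ml are recorded. The exclusion of volume stands only under Intra-operative Data; the post-operative transfusion item imposes no such rule.

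**3. Timing.** Randomisation follows separation from bypass (Statistical Considerations, item 1) and may take place in the OR or the PICU (Study Procedures, item 1). Cell saver volume for the whole operation therefore includes loss before randomisation. For an infant randomised in the PICU, all loss from the initial operation comes before assignment. Adding the volume field repairs the definition; only the part collected after randomisation can reflect treatment.

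**4. Study-product volume.** Inputs: concentrate at 70 mg/kg (Statistical Considerations, item 1), concentration 20 g/L, which is 20 mg/ml (Background), and "Cryoprecipitate group (dose: 10 ml/kg; active control group".

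- Concentrate: 70 / 20 = 3.5 ml/kg.
- Difference from cryoprecipitate: 10 − 3.5 = 6.5 ml/kg, and 6.5 / 10 = 65%.

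This contrast is fixed by the planned doses and can be derived from recorded weight. It is not a result that the data list loses.

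**5. Units against ml/kg, illustration only.** The documents give no transfused volumes, unit sizes, weights or SDs, so every input here is an assumption: 15 per arm, weights uniform from 3 to 12 kg, gamma-distributed volumes with means 30 against 15 ml/kg (SD 15) or 60 against 30 ml/kg (SD 30), whole units opened, Mann-Whitney test at 0.05, and 1,000 simulated trials per row.

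| Unit size | Means (ml/kg) | Power on ml/kg | Power on units | Loss (points) |
|---|---|---|---|---|
| 60 ml | 30 v 15 | 84.5% | 77.7% | 6.8 |
| 60 ml | 60 v 30 | 85.5% | 81.3% | 4.2 |
| 150 ml | 30 v 15 | 88.1% | 58.2% | 29.9 |
| 150 ml | 60 v 30 | 85.9% | 76.3% | 9.6 |
| 300 ml | 30 v 15 | 85.6% | 21.6% | 64.0 |
| 300 ml | 60 v 30 | 85.8% | 56.5% | 29.3 |

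The second pair of means is the first doubled, and unit size does not enter the ml/kg analysis. The six ml/kg figures thus estimate the same power and differ only by simulation error. The loss on units mixes two effects: rounding up to whole units, and leaving weight out of the count. It runs from about 4 to 64 points, depending on how large a unit is relative to what the infant receives.

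**The case against.** The cell saver entry stands under transfusion requirements and appears again among post-operative transfusions, so it may well mean blood returned to the infant, not blood collected as a measure of loss. On that reading the list does not forbid recording a collected volume. This is fair, but it leaves the gap where it was, because no other item collects that volume.

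Counting units is also a coherent choice. The sample size statement is framed as exposure to 2 additional allogeneic products, and the post-operative item treats a new unit as a new exposure. The Background gives infectious and immunological reasons for limiting allogeneic exposure. All of that stands. Unit counts should remain the exposure measure, and ml is an addition.

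A reader might infer that unit counting hides most of the transfusion difference between arms. The documents do not support this: they contain no volumes or unit sizes from which to judge, and in the illustration the loss is small when units are small. They also do not say that infants usually receive part of a unit, only that a unit may be used again.

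A reader might also infer that the trial fails to record the 65% difference in study-product volume. That difference is set by the doses and follows from recorded weight. Only the total volume across all products is affected.

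**Conclusion.** The mismatch is real and is established from the text alone, without assumptions. Followed as written, the data list leaves the intra-operative component of one secondary outcome without its input for all 30 planned infants. Chest drain output and the primary outcome are unaffected. The component would in any case carry limited information about treatment unless loss after randomisation can be separated from loss before it.

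The case for recording ml beside units is modest. It rests on the plan's own indication that one unit can serve more than one transfusion, and on the Background's interest in transfused volume. Its size cannot be stated from the documents, and the simulated losses hold only under their assumed inputs.

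**What to change.** - **Cell saver.** In Intra-operative Data, take cell saver out of the unit-count line and enter its volume in ml as a bleeding item. State whether blood collected or blood returned is meant, and use the same term in the outcome definition. Keep cell saver, which is the infant's own blood, out of every allogeneic total.
- **Timing.** Where the record allows, enter the volume collected after randomisation separately from the whole-operation total. If only the total is available, label it as including loss before randomisation.
- **Allogeneic products.** In both the intra-operative and post-operative lists, record ml given beside units, with units defined as new donor exposures and a stated rule for part-units. Report ml/kg by product descriptively, using the recorded weight. No further hypothesis test is needed.

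This changes the data form and a few lines of text. The cost is somewhat more abstraction time for about 30 infants. It assumes that the medical record holds the volumes and their times, which the documents do not confirm; a look at a few past charts before the form is fixed would settle that.

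### Data fields do not match the outcomes: re-exploration is recorded as ECMO, bleeding includes loss before treatment, and listed capture stops at 48 hours

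*Combined protocol and SAP*

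**What the plan says.** **Timing of treatment.** Study Procedures, question 1, says "Subjects will be monitored for 48 hours for the need for fibrinogen supplementation", without saying when the 48 hours begin. It goes on: "Once the need for fibrinogen supplementation is confirmed in the OR or PICU, subjects will be randomized into one of two treatment groups". Statistical Considerations, question 1, says "Once the need for fibrinogen supplementation is confirmed after separation from CPB, patients will be randomized", with no time limit.

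**Outcomes.** The primary outcome (Statistical Considerations, question 4) is "any allogeneic blood transfusion within the first 24 hours after administration of the FC or cryoprecipitate". Among the secondary outcomes (question 5) are "bleeding over the first postoperative 48 hours (intraoperatively = cell saver volume; postoperatively = chest drain/s output" and "the need for surgical re-exploration for hemostasis over the first postoperative 48 hours". Question 5 also follows individual blood products to 7 days, thromboembolic events to 7 days, and a clinical composite to 30 days or discharge if that comes sooner.

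**Data capture.** In the list of data to be obtained, item 3 is titled "Postoperative Data (PICU, up to 48 hours after surgery) collected from the medical record". One of its fields is "re-exploration? (= starting ECMO in the PICU". The list names no time for the study dose or for each transfusion, and it has no items for the 7-day or 30-day outcomes.

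**The concern.** An outcome can be analysed as defined only if the fields collected are able to produce it. Here the outcome definitions and the data list appear to have been written separately, and they disagree in three places.

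- The re-exploration field describes a different event from the re-exploration outcome.
- The bleeding outcome has its origin at surgery, whereas treatment starts later and at a time that varies between infants. Part of what is counted cannot have been affected by the treatment.
- Listed capture has a fixed end at 48 hours after surgery. The primary window moves with the treatment time, and several secondary windows are longer.

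At stake are the meaning of one secondary outcome, the precision of another, and whether the primary outcome is captured in full for any infant treated late. With 15 per arm, a few misclassified infants can change a comparison.

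**Working it through.** The plan gives no figure of its own on this point. The check compares passages and then does simple arithmetic on time.

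**1. Re-exploration**

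| Event | Counts under the outcome (question 5) | Counts under the data field (item 3) |
|---|---|---|
| Return to surgery for bleeding, no ECMO | yes | no |
| ECMO started in the PICU for a reason other than bleeding, no re-operation | no | yes |
| Return to surgery for bleeding, with ECMO started in the PICU | yes | yes |

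The two agree only in the third row. No assumption is needed.

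**2. Bleeding before treatment**

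Randomisation comes after separation from bypass, so cell-saver volume collected before separation is pre-treatment in every infant. For an infant randomised in the PICU, all cell-saver volume from the index operation and all earlier drain output are pre-treatment. Let *t* be hours from the end of surgery to the first study dose. The share of the 48-hour postoperative window that lies before treatment is *t*/48:

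- *t* = 6: 6/48 = 12.5%
- *t* = 12: 12/48 = 25%
- *t* = 24: 24/48 = 50%
- *t* = 36: 36/48 = 75%

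These are shares of hours, not of blood lost. The documents do not say how bleeding is distributed over time.

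**3. Capture against outcome windows**

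*Longer outcomes.* Seven days is 7 × 24 = 168 h, so listed capture leaves 168 − 48 = 120 h (5 of 7 days) of the product and thromboembolic outcomes uncovered. For the composite it leaves 30 − 2 = 28 of 30 days, or the time to discharge if shorter. Creatinine appears only among the preoperative laboratory values, although acute kidney injury is part of the composite.

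*Primary outcome.* Assume that the 48 hours of monitoring start at the end of surgery, so that *t* can reach 48. The window runs from *t* to *t* + 24, and the hours beyond listed capture are max(0, *t* + 24 − 48).

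| First dose at hour *t* | Window ends at hour | Hours beyond capture |
|---|---|---|
| 24 or earlier | 48 or earlier | 0 |
| 30 | 54 | 6 |
| 36 | 60 | 12 |
| 42 | 66 | 18 |
| 48 | 72 | 24 |

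Product capture to 168 h would cover the latest possible window end of 72 h.

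**The case against.** The strongest reply is that little may be lost in practice. Product data come from the medical record, administration of study drug is documented there (Subject Compliance with Study Procedures), and question 5 already asks for products to 7 days. If that is done with transfusion times, the primary window is covered for everyone. The inclusion criterion and Statistical Considerations, question 1, tie the decision to the period after separation from bypass, so many infants may be treated in the operating room. If the primary outcome is read as yes or no, one transfusion within the captured hours settles it. This stands, and it limits the third part to a contradiction between the data list and the outcomes.

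On bleeding, randomisation balances pre-treatment loss in expectation, and the outcome is secondary in a self-described pilot. That also stands. The harm is noise and chance imbalance, not systematic bias.

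Neither argument touches the re-exploration field, where an abstractor who follows the list records the wrong event.

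A reader might infer more than the documents support:

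- *That outcomes in general run from surgery and end at 48 hours.* The primary runs from administration, and several secondary outcomes run to 7 or 30 days. The general 48-hour stop belongs to the data list.
- *That every infant randomised in the PICU has a truncated primary outcome.* Treatment at hour 24 or earlier loses nothing.
- *That most of the measured bleeding precedes randomisation.* No passage gives that split.

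**Conclusion.** The point holds, with different certainty for its parts.

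- **Re-exploration:** wrong as written, with no assumption needed. Re-operations for bleeding without ECMO would be missed, and ECMO for another reason could be counted.
- **Bleeding:** the outcome includes loss before treatment for every infant with cell-saver volume collected before separation from bypass, and more for those treated in the PICU. The cost is precision in one secondary outcome with 15 per arm.
- **Capture:** the 48-hour limit contradicts the 7-day and 30-day outcomes outright. Against the primary outcome the shortfall is conditional. It requires monitoring to start at the end of surgery and affects only infants treated after hour 24, by up to 24 hours each. Their number is not stated, so no study-level effect or loss of power can be given.

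It would go too far to say that late-treated infants lose primary data. The record may hold the data; the listed capture does not ask for them.

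**What to change.** 1. Replace the re-exploration field with two: surgical re-exploration for bleeding (yes/no, time) and ECMO started (yes/no, reason).
2. Count the bleeding outcome from the start of the first study-product dose. Where earlier loss can be separated, use it only as a baseline covariate. The tests named in Statistical Considerations, question 2, are unadjusted, so the adjusted analysis needs a sentence there.
3. Record the time of the first study dose and of every transfusion, including those in the operating room.
4. State when the 48 hours of monitoring begin.
5. Extend product capture to 7 days, which also covers 24 hours after any dose given within 48 hours of surgery. Add items for the 7-day thromboembolic outcome and the 30-day composite, abstracted from the existing record.

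The cost is revised outcome wording, a few form fields and some added chart abstraction. Patient care and sample size do not change.
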